COVER PAGE

Official Title:

"Feasibility and safety of an over-pressure wash-in method using fresh gas flow 0.5 L and Sevoflurane 8% during initiation of low-flow anaesthesia: a prospective, randomised, descriptional study".

Proposal ID: MoH/CSR/23/27624

The study proposal was approved by the Health Studies and Research Approval Committee (HSRAC), Ministry of Health, Sultanate of Oman dated 26/12/2023.

Date: 01-01-2024

Title

Feasibility and safety of an over-pressure wash-in method using fresh gas flow 0.5 L and Sevoflurane 8% during initiation of low-flow anaesthesia: a prospective, randomised, descriptional study

Introduction and review of literature

Low-flow anaesthesia (LFA) with fresh gas flow (FGF) ≤ 1 L/min has advantages due to relatively lower cost, less environmental burden, and increased humidity and temperature of inspired gas leading to improved mucociliary function of the patient.¹ Any technique that employs a fresh gas flow that is less than the alveolar ventilation can be classified as LFA. The development of modern anaesthetic machines, gas analyser monitors, precision vaporisers and introduction of more potent volatile agents with minimal uptake were some of the breakthroughs encouraging LFA enthusiasts.² The staggering amount of environmental pollution due to anaesthetic gases during the present-day practice virtually mandates every anaesthesia provider to take that extra bit of effort to use the available facilities to implement LFA.³ The idea of LFA is to replenish the consumed gases with as minimum fresh gas as possible while making sure to remove CO₂ before recirculating. This minimises the loss of anaesthetic agents into the environment.⁴ The merits of reducing flow must not overrule safety, by maintaining adequate oxygen content in the circle and avoiding hypoxic gas mixture, inadequate anaesthesia control and too light anaesthesia with risk for awareness.², 5

Volatile anaesthetic agents are unique in that it is possible to significantly reduce the mass of drug delivered to the circuit (by lowering FGFs) without altering the amount that actually enters the patient.⁶ Studies have shown that 1 L/min change in FGF with Sevoflurane results in a change of between 4 and 18 ml/hour consumption of sevoflurane.⁷ The challenge is to control the dynamic equilibrium of FG composition as the uptake and metabolism are time-sensitive and many factors influence the consumption and production of gaseous components. This can be achieved only through frequent adjustments in the gas flow controls.¹

LFA requires flow meters calibrated to low flow down to 50 ml/min, leak-proof circle breathing system and airway devices like cuffed endotracheal tube (ETT), gas monitoring system providing inspired and end-tidal concentrations of agent, vapourisers capable of delivering high concentrations and calibrated to be accurate at low FGF. Since low FGFs are added to significantly large reserve volume (approximately 9-10 litres), consisting of breathing tubing, reservoir bag, anaesthetic ventilator, intergranular space, etc., in addition to functional residual capacity (FRC) of the patient, it requires 3time constants (calculated by reserve volume divided by FGF) to effect 95% change in gas composition to occur. However, once steady state is achieved, LFA provides the most economic use of anaesthetic agents. Sevoflurane when used with strong base-free CO₂ absorbent is suitable for use in LFA because it has low blood-gas solubility. The minimum alveolar concentration (MAC) of Sevoflurane varies with patient age, from 1.4% at age 80 years to 2.3% at age 1 year.8 The optimal alveolar concentration of Sevoflurane (FAS) to prevent motor movement and autonomic response during anaesthesia is MAC-Bar which approximates 1.5 MAC. Thus, the target of FAS during anaesthesia in daily practice varies between 1 to 3.5%, depending on the adjuvant drugs used.

Since use of low FGF leads to a long time constant, a wash-in phase using a high FGF and high vapouriser concentration (Fv) of volatile anaesthetic is warranted in order to rapidly achieve the required concentration of inhalation anaesthetic in the breathing system.⁸ Conventionally LFA is administered using high flows initially up to 4-10 L/min for 3-time constants (approximately 3 minutes) with Sevoflurane dial setting of 0.8-2.5% to bring the circuit to the desired concentration, then the flows are reduced for maintenance of anaesthesia. In this method of initial high flows, there is risk of delivering high anaesthetic concentrations during induction of anaesthesia and wastage of volatile agents when the total consumption of anaesthetic agent (AA) is calculated at the end of surgery.

Wash-in is the time taken to reach 1 MAC concentration. Sevoflurane wash-in schemes lack simplicity, target coverage and applicability. Various studies have demonstrated that the time to reach 1 MAC decreased at higher flow rates (1-2-4) but plateaued at 4-4.8 L/min. Lindqvist et. al.9 reported a 2-step wash-in technique to achieve a FAS of 1.2%; starting with FGF 1 L·min-1 and FvS 8% for 1 min, then reducing FGF to 1, 0.7, 0.5, and 0.3 L \cdot min-1. They found that the respective time to achieve the target FAS was 1.8, 1.5, 2.5 and 3.6 min. Horwitz et. al.10 reported that by using a FGF of 1.0 or 0.5 L·min-1 with a FvS 6% during the wash-in, the respective time to reach 1 MAC was 6.2 ± 1.3 and 15.2 ± 2.4 min and up to 1.5 MAC at 7.5 ± 2.5 and 19 ± 4.4 min. Shin et al.11 performed a wash-in study using a Primus anaesthetic machine connected to a test-lung, using a FGF of 0.5, 1, and 3 L·min-1 and setting the FvS to 6%. The respective mean time to reach a FAS of 4% for each FGF was 1165, 534, and 155 s. Nel MR et. al. 1_2 have shown while using FGF=6 L (Nitrous Oxide 4L + O₂ 2L) and Sevoflurane vapouriser dial set at 2.5% that equilibration point defined as FE/FI=0.8 (corresponding to FAS=2%) can be reached in a mean (standard deviation) of 8.2 ± 2.1 min. Tribuddharat S et. al.8 studied the 1-1-8 wash-in scheme with FGF=2L (O₂ 1 L + Air 1 L) and FvS 8% which yielded a respective FaS of 1, 1.5, 2, 2.5, 3, and 3.5% at 1, 1.5, 2, 3, 3.5, and 4.5 min when used with N2O and at 1, 1.5, 2, 3, 4, and 5 min when used with air.

In a test lung model study Jakobsson et. al.4 reported wash-in with a respective FGF of 0.3 and 4 L·min-1 and a FvS of 8%. They found that the FaS reached 1 MAC (2.1%) at 547 ± 83 and 38 ± 6 s, respectively. It was possible to increase the AA concentration from 0 to 1 MAC value in around one minute by using a FGF of 4–4.8 L/min using a fixed dial setting of 3 MAC, but raising the FGF further did not result in shorter wash-in times. Wash-in times were significantly faster with higher flow rates for FGF spanning from 1, 2 and 4 L/min, however a plateau started at FGF 4–4.8 L/min, where increasing the FGF further up to 6 or 8 L/min did not shorten the time to reach 1 MAC significantly.¹³

The conventional method which uses initial high FGF during the wash-in phase defeats the purpose of LFA such as conservation of gases, reduced environmental pollution and economical savings even

though it provides a more stable gas composition within the breathing system. Beginning of anaesthesia is also a task-intense phase requiring multiple tasks to be performed to ensure the patient safety. Any additional tasks during this phase may have high chances of being forgotten with a potential for compromised patient safety. Therefore, the technique has to be simple to execute. We wish to evaluate a technique of initiating Sevoflurane LFA which is simple, has a quick wash-in and minimises gas consumption without compromising the safety when compared to conventional method of attaining LFA using initial high flows.

Methods

After obtaining the approval from the Institutional Ethics Committee of The Royal Hospital, Muscat, we will register this prospective, randomised, descriptive study in an appropriate online clinical trial registry. A written informed consent will be obtained from all the patients. Forty-eight patients of either gender aged 18-65 years, with American Society of Anesthesiologists (ASA) physical status of 1-2, undergoing elective surgery with the expected duration more than 1 hour under general anaesthesia requiring endotracheal intubation will be included. Pregnant women, smokers, patients with a body mass index (BMI) \geq 30 kg/m₂, cardiac/pulmonary/renal or liver impairments, upper or lower respiratory infections within the past 6 weeks and anticipated difficult airway will be excluded.

Age, gender, height and weight of the patients will be recorded. All the patients will follow the standard fasting requirements and receive no sedative premedication. They will be randomised before entering the operating room into one of the two groups, 'conventional group' (Group C) and 'over-pressure group' (Group OP), using block randomisation technique with varying block sizes. An appropriate intravenous cannula will be secured in the operating room and Ringer's Lactate 500 ml will be started. The patients will receive standard anaesthetic care and intra-operative monitoring with electrocardiogram, pulse oximeter (SpO₂), non-invasive blood pressure (NIBP) and capnography. Avance CS₂ anaesthesia workstation (GE Healthcare, Madison, WI, USA) which has an integrated anaesthetic gas analyser, displays age-adjusted MAC according to the internal algorithm and returns sampled gas to the breathing system will be used in this study. The breathing system will consist of a 2 L reservoir bag, disposable breathing circuit, heat-moisture exchanger and standard circle system with Sodalime as the CO₂ absorbent. The workstation will be tested to ensure no leak in the system and vapourisers are calibrated.

Ideal Body Weight (IBW) of the patient will be calculated based on the following formula: IBW (kg)=50 + 0.91 (height in cm – 152.4) for Men and 45.5 + 0.91 (height in cm – 152.4) for Women. The ventilator will be preset in Pressure Control-Volume Guarantee (PCV-VG) mode with a tidal volume of 8 ml/kg of IBW, respiratory rate=14 breaths/min, positive end-expiratory pressure (PEEP)=5 cmH₂O and an inspiratory:expiratory ratio of 1:2. The set minute volume will be noted. The alarm for end-tidal Sevoflurane (FAS) will be set at 2% to alert the clinician.

Heart rate (HR), blood pressure (BP) and peripheral oxygen saturation will be recorded before induction of anaesthesia, every minute until 5 min after induction and every 5 min intervals thereafter. The FGF will be set at 6 L/min with 100% O₂ during pre-oxygenation and manual ventilation. Following pre-oxygenation for 3 min, general anaesthesia will be induced with intravenous Fentanyl 2 μ g/kg followed by Propofol 2 mg/kg administered over 30 seconds and Rocuronium 1 mg/kg for neuromuscular blockade. Lungs will be ventilated manually and propofol 20 mg every minute will be administered until tracheal intubation. Tracheal intubation with an appropriate size ETT will be performed 90 seconds later, the cuff inflated to 25-30 cmH₂O using a cuff-pressure monitor device and ETT secured with an adhesive tape. The correct ETT position will be confirmed by auscultation and square-wave capnograph. FGF will be paused during intubation and restarted after inflating the ETT cuff. The FGF hereafter will consist of O₂ and Air with a set F₁O₂=0.6. FGF and Sevoflurane vapouriser dial (FvS) will be set as per the group allocation and mechanical ventilation will begin. The time of opening of vapouriser will be considered T_{zero}.

Following will be the steps during wash-in for achieving LFA:

The 'conventional' group (Group C): FGF will be set to 6 L/min and the FvS 3% at T_{zero}. The FGF will be reduced to 0.5 L/min upon reaching FaS 2%. Hereafter, the FvS will be set to 4% and maintained till 15 min (T₁₅) from T_{zero}.

The 'over-pressure' group (Group OP): FGF will be set to 0.5 L/min and FvS 8% at Tzero. Subsequently, the FvS will be set to 4% upon reaching FAS 2% and maintained till 15 min (T15) from Tzero.

The time of reaching $F_AS=2\%$ will be noted in both the groups. The time taken in seconds from T_{zero} to reach $F_AS 2\%$ (T_{target}) will be calculated. Inspired concentration of Sevoflurane (FiS), FaS, and age-adjusted MAC will be retrieved from the automatically recorded 'trend' of parameters. FiS, FaS and age-adjusted MAC will be noted every 30 sec. starting from T_{zero} , till T_5 and every minute thereafter until T₁₅.

Consumption of gases (Oxygen, Air and Sevoflurane) from the beginning until T₁₅ will be retrieved. Any reduction in mean BP >20% from the baseline will be treated with intravenous Ephedrine 12 mg bolus and consumption of Ephedrine will be noted. Expired minute volume (MV_E) at T_{target} and T₁₅ will be noted. The study period will end at T₁₅ in both the groups. Painting the surgical parts and draping will be permitted during the study period. Care will be taken to avoid any activity which risks ETT disconnection during the study period. Subsequent management of anaesthesia will be left to the discretion of the attending Anaesthesiologist.

For both the groups, 'stability of Sevoflurane concentration', defined as FAS in the target range of 1.6-2.4% during the time interval from T_{target} till T₁₅ will be assessed. The investigator will be allowed during this period to increase or decrease if needed the vapouriser dial by 1% at a time every 2 min to keep the FAS in the target range. The number of times the vapouriser dial is adjusted will be noted. The system will be considered 'stable' if the FAS is maintained in the target range without the need for dial adjustment and 'unstable' if vapouriser dial adjustment is needed at any time during this period.

Delivery of Oxygen will be monitored to ensure at least 300 ml/min and delivered F_1O_2 at least 0.3 at all time. The investigator will be allowed to increase if needed the set F_1O_2 by 0.1 at a time every 2 min to keep the delivered $F_1O_2>0.3$. The number of times the set F_1O_2 is adjusted will be noted. End-tidal carbon dioxide (ETCO₂) will be maintained between 30 and 40.

The aim of the study is to assess during the wash-in phase of LFA the feasibility of the method, stability of the system and consumption of gases. The primary outcome will be the time required to achieve FAS 2%. Secondary outcomes will be the stability of the system assessed by the number of times vapouriser dial and the set F1O₂ adjusted, consumption of gases and of ephedrine.

Statistical analysis

Sample size is calculated based on a previous study₈ which showed the 1-1-8 wash-in scheme with FGF=2L (O₂ 1 L + Air 1 L) and Sevoflurane dial at 8% yielded an F_AS of 2% at 2 ± 0.5 min. Hence, we assume that with our wash-in technique using FGF=0.5 L (O₂ + Air) and FvS 8% the time needed to reach F_AS=2% will be around 8 min. To detect a difference of 2 min (25%) with standard deviation (SD) of 2 using an alpha level of 0.05 and a power of 0.90 the sample size needed is 22 per group. For a possible 10% dropouts, it is decided to include 24 patients per group.

Statistical analysis will be carried out using an appropriate statistical software. Data will be presented as mean \pm SD or median (range). Intergroup differences will be assessed for significance using Student's t, Kruskal-Wallis, chi-squared or Fisher exact tests, as appropriate. P < 0.05 will be considered statistically significant.

Study duration: Approximately 8 months (from December 2023 to July 2024). Data collection: December 2023-May 2024, statistical analysis and writing manuscript: June-July 2024.

How will the expenses be met with? : Does not involve any additional expenditure.

Department associated in the study: Department of Anaesthesia and Intensive Care, Royal Hospital, Muscat.

References

1. Baum JA. Low-flow anesthesia: theory, practice, technical preconditions, advantages, and foreign gas accumulation. J Anesth. 1999;13(3):166-74. doi: 10.1007/s005400050050. PMID: 14530937.

4. Jakobsson P, Lindgren M, Jakobsson JG. Wash-in and wash-out of sevoflurane in a test-lung model:
A comparison between Aisys and FLOW-i. F1000Res. 2017 Mar 29;6:389. doi: 10.12688/f1000research.11255.2. PMID: 28529707; PMCID: PMC5414818.

5. Feldman JM. Managing fresh gas flow to reduce environmental contamination. Anesth Analg. 2012 May;114(5):1093-101. doi: 10.1213/ANE.0b013e31824eee0d. Epub 2012 Mar 13. PMID: 22415533.

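### Patients are randomised before theatre although the allocation is first used after intubation, and the time of disclosure is not fixed; allocating just before T_zero would be a cheap improvement

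*Protocol*

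**What the plan says.** All references are to the Protocol.

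- **Methods, randomisation.** "They will be randomised before entering the operating room into one of the two groups", "using block randomisation technique with varying block sizes".
- **Methods, induction.** One procedure serves both arms: "The FGF will be set at 6 L/min with 100% O₂ during pre-oxygenation and manual ventilation", then induction drugs at fixed weight-based doses, then "Lungs will be ventilated manually and propofol 20 mg every minute will be administered until tracheal intubation". Intubation, cuff inflation and confirmation of tube position follow.
- **Methods, start of wash-in.** Only then do the arms part: flow and vapouriser dial "will be set as per the group allocation and mechanical ventilation will begin". On the clock: "The time of opening of vapouriser will be considered" T_zero.
- **Methods, outcomes.** The primary outcome is the time from T_zero to an end-tidal sevoflurane of 2%. Ephedrine and gas consumption are secondary. Gas is counted from a beginning that is not tied to T_zero, and no starting point is given for the ephedrine count.
- **Statistical analysis.** The requirement is 22 per group. "For a possible 10% dropouts, it is decided to include 24 patients per group".

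The protocol does not state who learns the allocation or when, and it describes neither blinding nor concealment.

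**The concern.** Nothing done between randomisation and T_zero needs the allocation, so randomising early gains nothing. It has two possible costs.

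1. **Losses after randomisation.** A case cancelled on the day, or an unexpected airway problem that changes the plan, leaves a randomised patient with no T_zero and so no primary outcome. The loss has nothing to do with either wash-in method, yet it uses up the dropout allowance and disturbs the balance that the blocks are meant to give. A statistical analysis plan could decide how to count such a patient, but it could not supply the missing outcome or move the point of randomisation.

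2. **A window in which the arm may be known.** If the allocation is disclosed when it is made, the operator could know it while deciding whether a patient stays in the study, while giving top-ups, and while treating any early fall in blood pressure. The items exposed are retention, the number of propofol top-ups, any ephedrine given before T_zero, and gas consumption if its count starts before T_zero.

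**Working it through.** **Order of events (Methods)**

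| Step | Differs by arm? |
|---|---|
| Randomisation, before the operating room | allocation made |
| Cannulation, pre-oxygenation at 6 L/min, induction, manual ventilation with top-ups | no |
| Intubation, cuff inflation, tube confirmation | no |
| Flow and dial set, vapouriser opened (T_zero) | yes, first use |
| T_zero to T15 | yes |

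Any loss in the second or third row is a randomised patient without a primary outcome.

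**The plan's own sample size**

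Inputs (Statistical analysis): difference 2 min, SD 2 min, alpha 0.05, power 0.90. The sidedness is not stated; two-sided reproduces the stated figure.

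n per group = 2 × (1.960 + 1.282)² × 2² / 2² = 21.01, rounded up to 22. This matches.

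Allowance: 24 − 22 = 2 patients per group. A third loss in one arm takes that arm below the protocol's own requirement. A full 10% loss leaves 24 × 0.9 = 21.6 per group on average.

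**Precision and power if losses before T_zero used the whole allowance**

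95% half-width = t(0.975, 2n − 2) × 2 × √(2/n)

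- n = 22: 2.018 × 0.6030 = 1.217 min
- n = 21.6: 2.019 × 0.6086 = 1.229 min
- Difference: 0.012 min, or 0.7 seconds

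The comparator is 22, because the patients above 22 were added to be lost. Against all 24 (1.162 min) the difference is 0.067 min, about 4 seconds.

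Power for a 2 min difference:

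| Analysed per group | Normal approximation | t test |
|---|---|---|
| 24 | 93.4% | 92.4% |
| 22 | 91.3% | 90.0% |
| 21.6 | 90.8% | 89.4% |
| 21 | 90.0% | 88.5% |
| 20 | 88.5% | 86.9% |

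The protocol does not say what share of dropouts would arise before T_zero. The cost therefore runs from nil to the 21.6 row if the 10% allowance is not exceeded.

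**Secondary outcome most open to events before T_zero**

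The start of the gas count is undefined. *If* it includes manual ventilation, one extra minute at 6 L/min adds 6 L of fresh gas. The over-pressure arm's whole flow from T_zero to T15 is 0.5 × 15 = 7.5 L. On that reading, even a small difference between arms before T_zero would show. If the count starts at T_zero, this route is closed.

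**The case against.** The case for leaving the rule alone is substantial, and much of it stands.

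- **A reader might infer that operators know the arm during induction. The document does not say so.** It fixes when patients are randomised, not when or to whom the allocation is revealed. The allocation could be held back until T_zero. Only *may know* is supported.
- **A reader might also infer that eligibility depends on a successful intubation on a leak-free circle. It does not.** The stated criteria can all be judged before theatre, the workstation is leak-tested, and an anticipated difficult airway is excluded. What remains is cancellation and the unanticipated.
- **The route to bias is narrow.** Induction is scripted, with fixed weight-based doses, a fixed top-up interval and a set time to intubation. Ephedrine has a numerical trigger and a fixed bolus. The primary outcome is an analyser reading counted from T_zero, and no path from induction behaviour to it is shown. If the arm is undisclosed, losses before T_zero should be unrelated to it; they would cost a little precision and cause no bias.
- **Later allocation does not protect ephedrine use throughout.** The operator sets the flow and dial, and so knows the arm from T_zero to T15 whatever is done earlier.
- **The change adds a step.** The Introduction itself warns that extra tasks at the start of anaesthesia may be forgotten, with a risk to safety.

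These points limit the size of the concern. They do not give a reason for randomising early, since no step before T_zero uses the result.

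**Conclusion.** The concern holds as a modest design improvement. The stated time of randomisation is earlier than the design needs. It turns any failure before T_zero into a loss after randomisation, and with no disclosure time fixed it leaves a window in which knowledge of the arm could affect retention, top-ups, early ephedrine and, on one reading, gas consumption.

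The numerical cost is negligible: 0.7 seconds in the half-width against plan, and power of about 89% by t test or 91% by normal approximation after a full 10% loss. The reason to act is clean accounting of randomised patients and protection of secondary outcomes, not sample size.

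This rests on three assumptions: the protocol's SD of 2 min, a two-sided test, and total losses within the 10% allowance. The share of losses before T_zero and the practice of disclosure are unknown. The protocol does not contradict itself here, and its figure of 22 per group is reproduced.

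**What to change.** Replace the randomisation timing in Methods with wording such as:

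*The concealed allocation will be opened only after tube position is confirmed and the cuff inflated, immediately before FGF and FvS are set, by a person already present to record data. Consented patients who do not reach this point are not randomised and do not count toward the 48.*

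The varying-block scheme, the total of 48 and all clinical steps stay as they are.

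**What it achieves.** It removes dropout before T_zero and knowledge of the arm before T_zero, and nothing beyond that.

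**Cost.** One sentence in the protocol and no added assessment. The downside is one more step in a phase that the protocol itself regards as task-heavy, which is why someone other than the operator should open the allocation. A few more patients may be consented than randomised.

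### Does ending observation at 15 minutes leave the primary outcome unanalysable for patients who never reach end-tidal sevoflurane 2%?

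*Protocol*

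**What the plan says.** The Methods define T_target as the seconds from opening the vaporiser to end-tidal sevoflurane (FAS) 2%, and state "The primary outcome will be the time required to achieve FAS 2" per cent. Concentrations are read every 30 seconds to 5 minutes "and every minute thereafter until T₁₅", and observation closes there: "The study period will end at T₁₅ in both the groups". Anaesthesia after that is at the attending anaesthesiologist's discretion.

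Stability is judged over the interval from T_target to 15 minutes. A system is stable "if the FAS is maintained in the target range without the need for dial adjustment" and unstable if the dial has to be adjusted in that interval. The aim covers "the feasibility of the method, stability of the system and consumption of gases".

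Under Statistical analysis, the sample size rests on a comparison of means: "To detect a difference of 2 min (25%) with standard deviation (SD) of 2", with alpha 0.05 and power 0.90, giving 22 per group, raised to 24 for dropout. The expected time in the over-pressure group is about 8 min. Data are to be summarised as mean ± SD or median (range). The test is left open: "Intergroup differences will be assessed for significance using Student's t, Kruskal-Wallis, chi-squared or Fisher exact tests, as appropriate".

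**The concern.** T_target is a time to event with a fixed end of observation. A patient below 2% at 15 minutes is right-censored: the time is known only to exceed 15. A mean, an SD and a t test need a number for everyone, so in practice such a patient would be dropped or given an arbitrary value. The same patient has no interval from T_target to 15 minutes, and so is neither stable nor unstable as defined.

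The loss would be one-sided. The Introduction cites 8.2 ± 2.1 min to FAS 2% at 6 L/min with a 2.5% dial. The conventional group uses 6 L/min at 3%, so it should nearly always reach target. Non-reachers would fall in the over-pressure group, and leaving them out would shorten that group's mean and flatter the new technique. It would also hide direct evidence on feasibility, namely how many patients reached 2%. The worry has a source in the protocol: for flows of 1.0 and 0.5 L/min at a 6% dial, the Introduction reports that "the respective time to reach 1 MAC was 6.2 ± 1.3 and 15.2 ± 2.4 min".

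**Working it through.** **The plan's own figure.** Inputs: difference 2 min, SD 2 min, two-sided alpha 0.05, power 0.90.

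n per group = 2 × (1.960 + 1.282)² × (2/2)² = 21.01, rounded up to 22. The stated size is reproduced. Power from the noncentral t is 0.900 at 22 per group and 0.924 at 24.

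**Formulas for non-reaching.** Assume normal times with mean m and SD s, and let a = (15 − m)/s.

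- Chance that one patient fails: p = 1 − Φ(a)
- Chance of at least one failure among 24: 1 − (1 − p)²⁴
- Amount by which the mean is too low if non-reachers are dropped: s × φ(a)/Φ(a)

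**At the planning values (8 ± 2).** a = 3.5, p = 0.023%, expected number 0.006 of 24, chance of any 0.6%, bias 0.002 min.

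**Conventional group, from the cited 8.2 ± 2.1.** a = 3.24, p = 0.06%, expected number 0.014 of 24.

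**If the planning mean is too low.** The cited 6% dial result must be moved to an 8% dial, which is an assumption whichever way it is done. Vapour delivered at 0.5 L/min is 30 ml/min at 6% and 40 ml/min at 8%. 1 MAC is taken as 2.0% unless stated.

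*Proportional scaling, from the 0.5 L/min result alone.* 15.2 × 30 = 456 ml, and 456/40 = 11.4 min.

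*Fit to both flows of that study.* At 1.0 L/min, 6.2 × 60 = 372 ml. So the volume needed is not a fixed 456 ml: it falls when delivery is faster. Taking a fixed volume plus a constant loss rate, loss = (456 − 372)/(15.2 − 6.2) = 9.33 ml/min and fixed volume = 372 − 6.2 × 9.33 = 314 ml. At 40 ml/min the time is 314/(40 − 9.33) = 10.2 min. If 1 MAC is 2.1%, as in the test-lung result in the Introduction, it is 10.2 × 2.0/2.1 = 9.8 min.

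The SD is either shortened in the same ratio as the mean or left at 2.4.

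| Over-pressure mean ± SD (min) | p | Expected of 24 | Chance of any | Bias if dropped (min) |
|---|---|---|---|---|
| 8 ± 2 (planned) | 0.02% | 0.006 | 0.6% | 0.002 |
| 9.8 ± 1.5 | 0.03% | 0.01 | 0.8% | 0.002 |
| 9.8 ± 2.4 | 1.4% | 0.35 | 29% | 0.09 |
| 10.2 ± 1.6 | 0.16% | 0.04 | 3.9% | 0.01 |
| 10.2 ± 2.4 | 2.4% | 0.57 | 44% | 0.14 |
| 11.4 ± 1.8 | 2.3% | 0.55 | 42% | 0.10 |
| 11.4 ± 2.4 | 6.7% | 1.6 | 81% | 0.33 |

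Other cited results at an 8% dial point the other way. The test-lung time of 547 s to 2.1% at 0.3 L/min (24 ml/min) scales to 547/60 × 24/40 × 2.0/2.1 = 5.2 min, without patient uptake. The two-step study (1.2% in 2.5 min) scales to about 5.8 to 7.5 min, depending on whether the first minute is counted.

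**Effect on the comparison.** A simulation with over-pressure 11.4 ± 2.4 against conventional 8.2 ± 2.1, 24 per arm, gave power 99.8% for the t test on complete data, 99.4% for the t test on reachers only, and 99.7% for Kruskal-Wallis with non-reachers tied last.

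**The case for a change.** The strongest case for a change is that 8 min is itself an extrapolation. It equals the cited 2 min at 2 L/min multiplied by four, that is, time inversely proportional to flow. The 6% dial study shows a steeper relation: halving the flow raised the time by 15.2/6.2 = 2.45. Applying that factor to both halvings from 2 to 0.5 L/min gives 2 × 2.45² = 12 min. At 12 ± 2, 1.6 of 24 would be expected to miss the target, with an 81% chance of at least one and a bias of 0.28 min. At 12 ± 3 the bias is about 0.86 min. With a true difference of 2 min and 22 per group, simulated power there is 0.27 for the t test on reachers against 0.56 for a rank test. The remedy would cost two sentences, and the stability definition that has no place for a non-reacher is in the protocol itself.

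Part of this stands. The censoring is real, the gap in the stability labels is real, and reporting how many patients reached 2% would serve the feasibility aim. But the harm needs both a mean well above plan and an analyst who drops non-reachers, which the protocol nowhere orders. A trial statistician faced with a missing T_target would take the listed rank test with that patient last, and could compare the proportions reaching 2% with the listed Fisher test. FAS is recorded to 15 minutes for everyone, so nothing needed is lost. Fixing a rank test in advance is not free either: at the planned 8 against 6 min, SD 2, its simulated power is 0.88 at 22 per group and 0.91 at 24. Calling a non-reacher unstable would also merge failure to wash in with drift after wash-in, which the protocol treats as separate matters.

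**Conclusion.** No change to the plan follows. The protocol is silent on a patient still below 2% at 15 minutes, but it prescribes nothing wrong: no test is tied to the primary outcome, suitable methods are on its list, and the handling rule belongs to ordinary analysis planning.

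On the protocol's own 8 ± 2 min the matter has no practical size (0.6% chance of any non-reacher among 24, bias 0.002 min). It becomes noticeable only if the true over-pressure mean is about 10 to 12 min with an SD of 2 or more. That rests on scaling a 6% dial result to 8%. The 42 to 81% risk from proportional scaling assumes a fixed vapour volume, which the same study's 1.0 L/min result does not support; fitting both flows gives about 10.2 min and a bias of 0.01 to 0.14 min. Even at 11.4 ± 2.4 min the bias is 0.33 min against a design difference of 2 min, and the simulated comparison is almost unaffected.

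These figures assume normal times and the scalings shown. If non-reachers do occur, reporting their number in each arm and keeping them apart from the stable and unstable counts is sensible practice within the present text.
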